9.3.5.3 Endpoints

The safety endpoint is to determine the safety of treatment with NFX-179 Gel ([REDACTED] and [REDACTED] or Vehicle Gel applied QD for 182 days of treatment. The results of dermal safety and local tolerability assessments including pain/burning, itching, erythema, edema, scabbing/crusting, and vesiculation/erosion will be summarized by treatment group and visit. The evaluation of adverse events will be based on summaries and listings of adverse events by treatment group, as described below under Safety Analyses. If tumor independence is confirmed as discussed above, the primary efficacy endpoint will be a dichotomized analysis conducted on the proportion of tumors achieving a reduction from baseline volume of at least 50%. A Chi-square analysis at the tumor level will be performed as the primary analysis between vehicle and each active treatment group. Otherwise, if tumor independence is not confirmed, the primary efficacy endpoint will be analyzed at the subject level. The primary efficacy analysis will then be a dichotomized Chi-square Responder analysis at the subject level. It will be based on the proportion of subjects considered to be Responders, where a Responder is defined as a subject

for whom at least 5 treated tumors showing the greatest tumor-level percent reduction from baseline volume have a percent reduction from baseline of at least 50%. A Chi-square analysis with contrasts as outlined above will be used. At the subject-level analysis, an Analysis of Variance will also be used to analyze the per-subject mean percent of tumor responders, with contrasts as described above. Treatment groups may also be compared using appropriate mixed-model logistic regression incorporating both tumor- and subject-level information. Supplementary analysis similar to those described above will also be conducted based on threshold reductions from baseline volume of at least 25%, 30%, 60% and 75%. The first secondary efficacy endpoint is to determine the clinical efficacy of NFX-179 Gel defined as the mean percent change in neurofibroma volume after 182 days of treatment based on tumor volume derived from ruler measurements. Analyses of Variance will be conducted both on the tumor level and the subject level, including the contrasts as described above. The determination of whether the tumor-level or subject-level analysis will be considered preferentially will be based on the outcome of the tumor independence assessment described above. The non-primary analysis will be considered as a supplementary analysis. Additional secondary efficacy endpoints include the analysis of change from baseline in the Physician's Tumor Assessment grade and the Subject's Self-Assessment grade after 182 days of treatment. These will be analyzed analogously to the primary endpoint using an Analysis of Variance and contrasts described above. In addition, for each assessment dichotomized analyses will be conducted on the proportion of tumors achieving a grade of Clear, the proportion of tumors achieving a grade of either Clear or Almost Clear, the proportion of tumors achieving at least a grade 1 improvement, and also a 2 grade or greater improvement from baseline after 182 days of treatment. Treatment groups will be compared using separate Chi-square analyses. An appropriate mixed-model logistic regression may also be used, as well as an ANOVA analysis of within-subject averaged results across tumors. Contrasts as described above will be used.

Analyses similar to those described above will be conducted based on tumor area and tumor length.

Efficacy analyses at post-baseline visits prior to Day 182 where efficacy data are collected will also be performed using the models described above. These will be considered exploratory in nature.

Analyses will also be performed to examine the strength of relationship between tumor volume Responders (as defined above), and PROM Responders defined as subjects indicating improvement based on Visit 8 Supplementary PROM items and also indicating the improvement was meaningful. These analyses will include appropriate correlation evaluations for dichotomous parameters, as well as odds-ratio analyses and related 95% confidence limits. These analyses will be conducted at both tumor and subject levels.

The psychometric properties of the PRO measure will be analyzed under a separate statistical analysis plan.

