	
(return to normal or to the baseline state) or until clinically stable as determined by the investigator.
 
Clinical Laboratory Safety Tests: At Visits 1, 2, 4 and 8 routine safety laboratory tests (CBC/differential, serum chemistry, and urinalysis) will be performed.
 
Local Tolerability: At Visits 2-9 local tolerability on each Target cNF will be evaluated through assessment of selected signs (i.e., erythema, edema, scabbing/crusting, vesiculation and erosion) and symptoms (i.e., stinging, burning and pruritus [itching]) of local tolerability.
 
Medical History: At Visit 1 medical history information will be reported for each subject. At Visit 2 medical history will be updated as needed.
 
Physical Examination: At Visit 1 a physical examination will be performed.
 
Vital Signs: At Visits 1, 2, 8 and 9 vital signs will be measured.
 
Pregnancy Tests: At Visits 1, 2, 4, 5, 6, 7, 8 and 9 female subjects who are women of childbearing potential will have a urine pregnancy test performed.
 
Efficacy Assessments:
 
Target cNF dimensions: At Visits 1, 2, 4, 5, 6, 7, 8 and 9 the investigator will measure the length, width, and height of each Target cNF using a ruler.
 
Physician’s Tumor Assessment: At Visits 1, 2, 4, 5, 6, 7, 8 and 9 the investigator will perform a Physician’s Tumor Assessment of the severity of each Target cNF.
 
Subject’s Self-Assessment: At Visits 2, 4, 5, 6, 7, 8 and 9 each subject will perform a Subject’s Self-Assessment of the severity of each Target cNF
 
Other Assessments:
 
Demographics: At Visit 1 demographic characteristics will be reported for each subject.
 
Pharmacokinetics: At select sites, blood samples for assessment of NFX-179 levels will be collected at Visit 4.
 
Patient Reported Outcome Measurements: At Visits 2, 6 and 8 each subject will perform a Patient Reported Outcome Measure assessment of each Target cNF.

--	--

	
Standardized Photography: At Visits 1, 2, 6, 8 and 9 standardized photographs will be taken of each Target cNF.

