5.6.9 Dose Modification

Subjects should not modify the study medication application procedure or frequency unless instructed to do so by the investigator. All application modifications must be reported on the appropriate CRF page.

If any significant study medication intolerance or safety issue occurs, after consulting with the Medical Monitor, the investigator or designee may direct the subject to reduce the study medication application frequency. If the subject cannot perform QD applications to a specific Target cNF(s), the subject may continue study medication treatment of <10 Target cNFs selected by the investigator for the duration of the study after consultation and approval from the Medical Monitor. If the subject cannot perform QD applications to any Target cNF for a total of 25 days,

the subject must be removed from the study. The total of 25 days applies to individual Target cNFs and is not an aggregate of non-treatment days of each Target cNF. Each Target cNF that meets or exceeds 25 total days of non-treatment cannot restart treatment. All 10 Target cNFs must be evaluated at each visit per protocol requirements regardless of study medication application frequency.

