7.1.3 Local Tolerability Assessment (LTA)

At Visits 2-9, the investigator and the subject will evaluate the signs and symptoms of irritation on each Target cNF using the LTA.

The LTA is the investigator's and the subject's assessment of the average overall severity of the signs and symptoms, respectively, associated with irritation on each Target cNF. The investigator and subject must NOT refer to any other evaluation to assist with these assessments. This is not a comparison with the assessment at any other time point.

The investigator will perform the LTA for signs using the scales below:

Erythema		
0	None	No erythema present
1	Mild	Slight red coloration
2	Moderate	Definite redness
3	Severe	Marked erythema, bright red to dusky dark red in color

Edema		
0	None	No edema
1	Mild	Slight, but definite edema
2	Moderate	Definite edema
3	Severe	Marked edema

Scabbing/Crusting		
0	None	No scabbing/crusting
1	Mild	Slight, but definite scabbing/crusting
2	Moderate	Definite scabbing/crusting
3	Severe	Marked scabbing/crusting

Vesiculation		
0	None	No vesicles
1	Mild	Small vesicles, no pustules
2	Moderate	Vesicles with pustules, transudate may be present
3	Severe	Pustules with transudate, vesicles may be present, may extend outside treatment area

Erosion		
0	None	No erosions
1	Mild	Slight erosion on treatment area
2	Moderate	Obvious erosion(s) on the treatment area
3	Severe	Marked erosion that may extend outside treatment area

The subject will perform the LTA for symptoms using the scales below:

Stinging		
0	None	No stinging
1	Mild	Slight stinging that is not bothersome
2	Moderate	Definite stinging that is somewhat bothersome
3	Severe	Intense stinging that causes definite discomfort and may interrupt daily activities and/or sleep

Burning		
0	None	No burning
1	Mild	Slight burning that is not bothersome
2	Moderate	Definite burning that is somewhat bothersome
3	Severe	Hot burning that causes definite discomfort and may interrupt daily activities and/or sleep

Itching		
0	None	No itching
1	Mild	Slight itching that is noticeable but not bothersome
2	Moderate	Definite itching that is bothersome but does not disrupt activities and/or sleep
3	Severe	Intense itching that is bothersome and may interrupt daily activities and/or sleep

The investigator will perform the LTA for signs for each Target cNF according to the following schedule:

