8.1 Definitions

8.1.1 Adverse Event (AE)

An AE is any untoward medical occurrence in a patient or clinical investigation subject administered a pharmaceutical product and which does not necessarily have a causal relationship with this treatment. An AE can therefore be any unfavorable and unintended sign or symptom associated with the use of an investigational product (including an abnormal laboratory finding), whether or not related to the investigational product.

Thus, any new, CR worsening of an existing sign, symptom, or disease, should be considered an AE.

Worsening of any Target cNF study assessment (e.g., LTA signs and symptoms) should be reported as an AE only if the use of the study medication is interrupted or discontinued or other therapy is required to manage the event.

Every new episode or clinically relevant worsening of a chronic condition (e.g., headaches, allergies, depression, and hypertension) should be reported as a separate AE, even if the condition is reported in the subject's medical history.

The investigator should, when certain, report a diagnosis rather than the signs, symptoms or clinically relevant abnormal laboratory values associated with the AE. Otherwise, signs, symptoms or abnormal laboratory values may be used to describe the AE.

An abnormality (*e.g.*, clinically relevant laboratory abnormalities) discovered prior to the first study medication application, should be reported as medical history, not as an AE.

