9.3.6 Safety Analyses

Subjects will be assessed for the occurrence of new and ongoing AEs. Descriptions of AEs will include the dates of onset and resolution (if resolved), maximum severity, seriousness, and action taken regarding the study drug, corrective treatment, outcome, and investigator's assessment of causality. All AEs will be recorded and classified using terminology from the Medical Dictionary for Regulatory Activities (MedDRA). All reported treatment-emergent AEs (TEAEs), defined as any AE with an onset on or after the date of first study drug application, will be summarized by treatment group, the number of subjects reporting TEAEs, system organ class, preferred term, severity, and relationship to study drug. When summarizing TEAEs by severity or relationship to study drug, each subject will be counted only once within a system organ class or a preferred term using the event with the greatest severity or causality, respectively, within each category. All reported SAEs will be summarized by treatment group, the number of subjects reporting SAEs, system organ class, preferred term, severity, and relationship to study drug.

All information pertaining to AEs noted during the study will be listed by subject and will include a verbatim description of the event as reported by the investigator, as well as the preferred term, system organ class, start date, stop date (if stopped), seriousness, severity, action taken regarding the study drug, corrective treatment, outcome, and relationship to the study drug. In addition, a listing of subjects who prematurely discontinued from the study due to AEs will be provided as well as a listing of subjects who reported an SAE.

Changes from baseline in safety laboratory values, local tolerability assessments, and vital sign measurements will be summarized with descriptive statistics for each treatment group at

all applicable study visits.

Shift tables will be presented for changes in safety laboratory values to summarize laboratory test results collected at all visits. Normal ranges established by the central laboratory will be used to determine the shifts. A listing of all out-of-range laboratory test results at any assessment time point will also be provided. Determination of clinical significance for all out-of-range laboratory values will be made by each investigator and included in the listing. In addition, a listing of all clinically significant laboratory test results will be provided.

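### The planned local tolerability summary lists items that do not match the LTA and need not show how many subjects ever had a moderate or severe reaction

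*Combined protocol and SAP*

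**What the plan says.** Section 7.1.3 sets out the instrument. At Visits 2 to 9 "the investigator and the subject will evaluate the signs and symptoms of irritation on each Target cNF using the LTA". There are eight scales, each graded 0 to 3. The investigator grades five signs (edema, erythema, erosion, scabbing/crusting, vesiculation) and the subject grades three symptoms (burning, itching, stinging). Stinging has its own anchors, from "Slight stinging that is not bothersome" at grade 1 to "Intense stinging that causes definite discomfort and may interrupt daily activities and/or sleep" at grade 3. Section 9.3.3 lists all eight as safety endpoints.

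Three statements cover how these data are summarized:

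- Section 9.3.5.3, with the same list in the synopsis: "local tolerability assessments including pain/burning, itching, erythema, edema, scabbing/crusting, and vesiculation/erosion will be summarized by treatment group and visit".
- Section 9.3.6, on changes from baseline: "local tolerability assessments, and vital sign measurements will be summarized with descriptive statistics for each treatment group", at each applicable visit. The synopsis says the same of local tolerability.
- The close of section 9.3.6, which says only that LTA data, among other safety assessments, are summarized by arm.

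On adverse events, section 8.1.1 says that worsening of a Target cNF assessment, with LTA signs and symptoms as its example, "should be reported as an AE only if the use of the study medication is interrupted or discontinued" or another therapy is needed to manage the event.

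**The concern.** Safety against vehicle is a primary objective (section 3), and the product is a gel applied to skin for 182 days. A reader of the report will want to know what share of subjects in each arm ever had a moderate or severe local reaction. The plan does not commit to producing that number. It also describes the tolerability table in terms that cannot be programmed from the instrument. Two of its labels correspond to no single scale, so someone would have to invent a rule for combining grades or decide which scale was meant.

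The LTA table carries particular weight because a reaction that changes no treatment is kept out of the adverse event tables by design. For such a reaction the LTA summary is the only place where it can be seen.

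**Working it through.** The plan gives no tolerability figure to reproduce, and the 90% power statement in section 9.1 plays no part here.

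**Step 1. Items side by side.**

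| LTA scale (7.1.3, 9.3.3) | Label in 9.3.5.3 and synopsis |
|---|---|
| Erythema | same |
| Edema | same |
| Scabbing/crusting | same |
| Itching (pruritus) | same |
| Burning | joined with pain, which has no LTA scale |
| Vesiculation | merged with erosion |
| Erosion | merged with vesiculation |
| Stinging | none |

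Four of the eight scales have a label of their own and four do not. Two of the six labels match no single scale. The only pain item scored per tumor is in the patient-reported outcome measure (7.3.3), an exploratory efficacy assessment taken at Visits 2, 6 and 8.

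**Step 2. What the summary statements fix.** They fix arm, visit and, in 9.3.6, change from baseline. They do not say whether the unit is the tumor or the subject, whether the statistics are means or grade frequencies, how 10 tumors combine within a subject, or how visits combine. The plan settles such questions elsewhere. Section 9.3.6 counts each subject once, at greatest severity, for treatment-emergent adverse events. Section 9.3.5.1 has a tumor-or-subject rule, but it covers efficacy measures only.

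**Step 3. Size of the dilution if means over tumors were used.** Inputs: 10 tumors per subject (4.1); top grade 3 (7.1.3); 50 completers per arm (synopsis, number of subjects). Assumptions: one scale, one visit, all baseline scores 0, a share *f* of subjects with one grade 3 tumor, and every other score 0.

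- Arm mean change = *f* × 3/10
- Share of tumors at grade 3 = *f*/10
- Share of subjects with worst grade 3 = *f*

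| *f* | Subjects affected of 50 | Mean change (0-3 scale) | Tumors at grade 3 | Subjects, worst grade 3 |
|---|---|---|---|---|
| 2% | 1 | 0.006 | 0.2% | 2% |
| 10% | 5 | 0.03 | 1% | 10% |
| 20% | 10 | 0.06 | 2% | 20% |
| 30% | 15 | 0.09 | 3% | 30% |

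For *f* = 20%, the grades sum to 10 × 3 = 30 over 50 × 10 = 500 tumors, and 30/500 = 0.06.

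**Step 4. Grade frequencies by visit.** These would show every grade 3 score, but not how many subjects ever had one. Suppose 2 of 50 subjects (4%) are at grade 3 at each of five visits. They could be the same 2 subjects (2/50 = 4% ever affected) or 10 different ones (10/50 = 20%). The by-visit tables are identical in both cases.

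**Step 5. The adverse event route.** Under 8.1.1, worsening that leads to no pause or stop of study medication and no other therapy is not an adverse event. Section 5.6.9 also allows a reduced application frequency, and it is not clear whether that meets the 8.1.1 condition; the two sections should be reconciled. The documents give no basis for estimating the share of reactions left out.

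**The case against.** Several stronger readings are tempting, and the documents do not support them.

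- *Stinging has been dropped.* It has not. It is collected at Visits 2 to 9 and listed in 9.3.3. The 9.3.5.3 list is open-ended and also covers dermal safety, and 9.3.6 refers to tolerability data without limiting the items. This is an inconsistency to reconcile.
- *Severe reactions are averaged away.* No section says that means are taken or that tumors are pooled. Descriptive statistics for a 0-3 scale can include frequencies and maxima, and either would reveal a grade 3 score. Step 3 therefore applies only if means are chosen, and its rates are assumed. It does not show that an active arm would look like vehicle.
- *Most such reactions will not be adverse events.* No figure supports this. Any reaction that leads to a pause, a stop or another therapy is reportable.
- *Tumors taken off treatment hide the harm.* Section 5.6.9 does say "All 10 Target cNFs must be evaluated at each visit per protocol requirements regardless of study medication application frequency", so a healing tumor keeps adding scores at later visits. But stopping treatment for irritation makes the event reportable under 8.1.1, and the earlier visit's table still holds the grade.

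The background evidence points both ways. In the 13-week minipig study, dose holidays for irritation fell particularly in the two groups whose dose levels were judged not tolerated (2.2.1). The sponsor's human study found few local signs and symptoms, almost all mild and transient (2.2.2), but it lasted 28 days against 182 here. Neither gives a rate for this trial.

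It is also fair to say that a worst-grade table loses timing, persistence and the number of tumors affected, and that one transient score can set a subject's grade. That argues for keeping the by-visit tables beside it. What stands against the plan is the mismatched list, the unstated unit and statistic, and the lack of any commitment to a per-subject worst grade.

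**Conclusion.** The point holds as a gap in specification. The item list in 9.3.5.3 and the synopsis contradicts the instrument and the plan's own endpoint list, which can be seen from the text alone. The stated summaries also need not yield the share of subjects who ever had a moderate or severe reaction, whether means or by-visit frequencies are used.

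How much would be hidden depends on choices the plan leaves open. With means over tumors and the assumptions of step 3, 20% of subjects affected appears as 0.06 on a 0-3 scale. With by-visit frequencies and the assumptions of step 4, the same tables fit anything from 4% to 20% ever affected. The adverse event tables cover only reactions that meet the 8.1.1 conditions, and the remainder cannot be sized from the documents. No efficacy analysis, sample size, alpha or power figure is affected. The change should be made because it is cheap and serves a primary objective.

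**What to change.** 1. In 9.3.5.3 and the synopsis, replace the six labels with the eight scales of 7.1.3 and 9.3.3.
2. In 9.3.6, add for each scale the worst post-baseline grade per subject across all Target cNFs and visits, with number and percent of subjects at each grade and at grade 2 or more, by arm. State whether the Visit 2 scores taken after the first application count as post-baseline.
3. Keep the by-visit summaries for timing and persistence, as grade frequencies, and state whether the unit is the tumor or the subject.

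The cost is a change of wording and one added table set from data already collected. The tolerability figures may look less favourable, and a single transient score can fix a subject's worst grade, which is why the by-visit tables stay.

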4 STUDY OVERVIEW

4.1 Study Design

This is a randomized, double-blind, vehicle-controlled, parallel group dose-response study evaluating the safety and effectiveness of 2 concentrations of NFX-179 Gel in subjects with cutaneous neurofibromas (cNF).

At Visit 1, the investigator will identify 10 Target cNFs that fulfill the enrollment criteria for treatment. The Target cNFs must be located on the subject's face, anterior trunk, or upper extremities. Preferably 2 Target cNFs are located on the face and 8 Target cNFs are located on the anterior trunk or upper extremities. Alternatively, at least 1 Target cNF is located on the face, in which case 9 Target cNFs must be located on the anterior trunk or upper extremities.

At Visit 2 (Day 1, Week 0) eligible subjects will be randomized and will begin the 182 day/26-week QD treatment period. The subject will apply the assigned study medication to the Target cNFs QD during the treatment period. The subject may have cNFs other than the Target cNFs but only the Target cNFs will be treated and evaluated.

Subjects will be seen at Visits 3-7 (Days 8, 29, 57, 85 and 141/Weeks 1, 4, 8, 12 and 20) for

follow-up visits during the treatment period.

At Visit 8 (Day 183/Week 26) subjects will be seen for the last treatment period visit and subjects will begin a 4-week no treatment follow-up period

At Visit 9 (Day 211/Week 30) subjects will be seen for an end of study visit.

No topical therapies for cNF other than the study medication may be used on any of the Target cNFs for the duration of the study.

As part of the clinical development program for NFX-179 Gel a subset of randomized subjects who complete this study (approximately 20%) may be invited to participate in an administratively separate exit interview study to learn about their experience in the study and to assist with their perception of clinically meaningful change in NF1.

A Coordinating Investigator, [REDACTED], is designated by the Sponsor. The Coordinating Investigator is responsible for the overall conduct of the study and signing the Clinical Study Report on behalf of the participating site investigators upon study conclusion.

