9.2 Randomization

Subjects will be randomized with a treatment allocation ratio of 1:1:1 (NFX-179 Gel [REDACTED] to NFX-179 Gel [REDACTED] to Vehicle Gel).

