9.3.5 Efficacy Analyses

9.3.5.1 Overview

Analyses of efficacy parameters collected at the tumor level will primarily be performed at the tumor level, under the assumption that tumor responses within the same subject will be predominantly statistically independent. Those parameters include results based on tumor dimensions, SSA and PTA evaluations, and responder analyses based on any of these measures. This approach is consistent with the topical application of the study medication to individual tumors and the assumption of minimal systemic absorption or systemic action of the study medication. The statistical assumption of within-subject tumor response independence will be evaluated using the appropriate Shrout-Fleiss intraclass correlation based on tumor changes from

baseline. For this study, that statistic is assumed to be less than 0.25. If this assumption is confirmed, analyses conducted at the subject level will then be performed as supplementary analyses. Tumor volume is the primary measurement of interest; however, the ruler measurements of tumor area, length, width and height will also be analyzed as supplementary analyses, using the analysis models applied to tumor volume.

If the Shrout-Fleiss intraclass correlation statistic is equal to or greater than 0.25, then subject-level efficacy parameter analyses will be considered primary, and tumor-level efficacy parameter analyses will be considered supplementary. In either case, results from both types of analyses will be presented.

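### The primary tumor-level chi-square ignores clustering of 10 tumors per subject whenever the ICC is below 0.25, so its error can run well above the stated 5%

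*Combined protocol and SAP*

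**What the plan says.** Treatment is assigned by subject. Section 9.2: "Subjects will be randomized with a treatment allocation ratio of 1:1:1". Section 4.1: "The subject will apply the assigned study medication to the Target cNFs QD during the treatment period". Section 5.6.9 adds: "All 10 Target cNFs must be evaluated at each visit per protocol requirements regardless of study medication application frequency". Each subject therefore contributes up to 10 outcomes under one treatment.

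Section 9.3.5.1 makes the tumor the default unit of analysis and says that independence "will be evaluated using the appropriate Shrout-Fleiss intraclass correlation based on tumor changes from" baseline. It continues: "For this study, that statistic is assumed to be less than 0.25". Below 0.25, independence counts as confirmed. At 0.25 or above, the subject-level analysis becomes primary.

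Section 9.3.5.3 gives the two primary tests. If independence is confirmed: "A Chi-square analysis at the tumor level will be performed as the primary analysis between vehicle and each active treatment group". If not, the primary test is a chi-square on the proportion of subjects with at least 5 tumors reduced by 50% or more. An ANOVA of the per-subject percent of responding tumors is also planned, and a mixed-model logistic regression is optional. The synopsis repeats the rule with the cut-off redacted.

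The rule reaches beyond the primary endpoint: "Those parameters include results based on tumor dimensions, SSA and PTA evaluations, and responder analyses based on any of these measures". Section 9.1 sets a two-tailed alpha of 0.05 and power of at least 90%.

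**The concern.** A Pearson chi-square on about 500 tumors per arm is valid only if tumors of the same subject are uncorrelated. An ICC estimate under 0.25 does not show that. Tumors of one subject share genotype, adherence, application technique and, by section 7, preferably the same assessor. Any positive correlation of the binary response makes the true variance of the tumor proportion larger than the test assumes. The p-value labelled primary then overstates the evidence, and a dose could be called better than vehicle more often than 1 time in 20 when it is not.

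Two further problems come from the same rule. First, the ICC form is not named, nor whether it is pooled over arms or computed within arm, so its strictness is undefined. Second, outcome data choose between two different quantities as primary: the percent of tumors responding, or the percent of subjects with at least 5 responding tumors.

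**Working it through.** **The plan's own figure.** The 90% power in section 9.1 can be neither reproduced nor refuted, because both response rates are redacted and the section does not say whether tumors or subjects were counted. With 50 subjects per arm and a binary subject outcome, 90% needs about 10% vs 37% or 20% vs 50%. With 500 independent tumors per arm it needs about 10% vs 17% or 20% vs 29%.

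**Inputs.** From the documents: two-sided alpha 0.05, 50 completers per arm, 10 tumors per subject, cut-off 0.25. Assumed: null response rates p of 10%, 20% and 35%; a normal model for tumor change with single-measure ICC ρ; ICC pooled over the three arms.

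**Formulas.** A tumor responds when its change falls below the p-quantile. With P11 the probability that two tumors of one subject both respond:

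- binary ICC = (P11 − p²) / (p(1 − p))
- design effect = 1 + 9 × binary ICC
- actual error = 2 × (1 − Φ(1.96 / √design effect))

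Example, p = 20% and ρ = 0.20: binary ICC 0.105; design effect 1 + 9 × 0.105 = 1.95; 1.96/√1.95 = 1.40; error 16.0%.

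The full rule was also simulated under the null (20,000 runs per setting, Monte Carlo SE up to 0.3 points), with ICC = (MSB − MSW)/(MSB + 9 MSW) estimated in each run. Below 0.25 the tumor chi-square was used; otherwise the 5-of-10 subject chi-square.

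| ICC of change | Binary ICC, p = 10/20/35% | Design effect | Error by formula | Error of full rule |
|---|---|---|---|---|
| 0.05 | 0.018/0.025/0.030 | 1.16/1.22/1.27 | 6.9/7.7/8.2% | 7.0/7.5/8.2% |
| 0.10 | 0.037/0.051/0.061 | 1.33/1.46/1.55 | 9.0/10.4/11.5% | 9.1/10.7/11.8% |
| 0.20 | 0.080/0.105/0.123 | 1.72/1.95/2.11 | 13.5/16.0/17.7% | 13.4/15.4/16.9% |

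At ρ = 0 the tumor chi-square returns 4.8–5.1%, as it should. At ρ = 0.01 the full rule gives 5.3–5.5%, so the excess is small near zero. At ρ = 0.20 about 97% of trials pass the check. At 0.24, 64–65% pass; error is 10.5–14.0% overall and about 15–19% among those passing.

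**Other readings.**

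- Average-of-10 ICC: a cut-off of 0.25 equals a single-tumor ICC of 0.25/(10 − 9 × 0.25) = 0.032. About 57% of trials pass at ρ = 0.03, 14% at 0.05 and almost none at 0.10. Error among passing trials is 5.3–6.3% for ρ from 0.01 to 0.05.
- Continuity-corrected chi-square, check not applied: 5.5–7.3% at ρ = 0.05 and 11.8–16.1% at 0.20.
- Percent volume change, not dichotomized: the design effect is 1 + 9ρ, which is 1.45 at 0.05 and 2.80 at 0.20, giving errors of about 10.4% and 24.2% for an unadjusted tumor-level comparison.

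**Tests that respect the subject.** The per-subject percent ANOVA (147 df) and a robust-variance comparison of the tumor proportion (between-subject variance per arm, 98 df) stayed at 4.8–5.3% in every null setting.

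**The case against.** The size of the excess rests on choices the documents do not settle. Under the null both arms respond at the vehicle rate, which is redacted, and a rate below 10% shrinks the problem. At 5% the formula gives 6.3% (ρ = 0.05) and 11.2% (ρ = 0.20). At 2% and ρ = 0.20 the binary ICC is 0.036, the design effect 1.32 and the error 8.8%. No expected ICC is given; 0.25 is a ceiling, and the average-of-10 reading brings error close to nominal. The normal model is untested for percent volume change built from 0.5 mm ruler readings. The rule is prespecified, the trial is Phase 2 with no multiplicity adjustment, and section 9.3.5.1 promises that "In either case, results from both types of analyses will be presented", so a valid subject-level p-value will be available.

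These points limit the magnitude and stand as such. They do not restore the 5% level: any positive binary ICC raises the error, and the plan names neither the ICC form nor a clustering adjustment. Forgoing multiplicity adjustment accepts several 5% tests, not one test at 13–17%. Presenting both levels does not change which p-value is primary. It is also fair to say that the choice between the two primary quantities is left to chance only when the true ICC lies near the cut-off.

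**Conclusion.** The point holds. When the ICC check passes, the primary test treats clustered tumors as independent, and nothing else in the plan corrects this. With a single-measure ICC, null rates of 10–35%, 50 subjects per arm and a normal model, the two-sided error per dose is about 7–8% at a change ICC of 0.05 and 13–17% at 0.20, against the stated 5%. The excess is smaller at lower response rates or under the average-of-10 form, and negligible if the true ICC is near zero. The direction does not depend on these assumptions as long as the binary ICC is positive.

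**What to change.** Remove the ICC rule and name one primary test that respects the subject as the randomized unit:

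- **Option A** keeps the tumor proportion: compare the proportion of Target cNFs with at least 50% volume reduction at Visit 8, each dose against vehicle, by GEE or a robust-variance chi-square clustered on subject, with a named small-sample correction.
- **Option B** makes the planned ANOVA of per-subject percent of responding tumors primary.

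A cluster-adjusted variance in the tumor-level branch alone would cure the error rate. Dropping the rule also stops outcome data from choosing the primary quantity. Treat percent change, PTA and SSA in the same way. Report the ICC descriptively, stating its form and whether it is pooled or within arm. Keep the unadjusted tumor-level and 5-of-10 analyses as supplementary.

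The change is to wording; no visits or data are added. Power must be recomputed by the sponsor with the redacted rates. At change ICC 0.20–0.24 and 50 per arm, simulated power (10,000 runs) is:

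| Vehicle vs active | ANOVA | Robust test |
|---|---|---|
| 10% vs 20% | 85–92% | 88–91% |
| 20% vs 35% | 94–97% | 94–96% |
| 10% vs 17% | 61–70% | 63–67% |
| 20% vs 28.8% | 57–64% | 58–63% |

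The last two rows are effects sized for 90% with 500 independent tumors per arm. There the unadjusted chi-square alone rejects in about 80–84%, but at inflated error.

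That is not the power of the plan as written. If the ICC is pooled over arms, a real effect raises it and pushes more trials to the weaker 5-of-10 test. In a separate set of 10,000-run simulations with ICC 0.24 and 10% vs 20% (other dose 10%), only 25% of trials pass; the full rule has 54% power, against 90% for the ANOVA and 87% for the robust test. At ICC 0.20 and 10% vs 17% (other dose 10%), the full rule has 76% against 71% for the ANOVA. So the change gains power in some settings and loses it in others. If recomputed power is below 90%, restate it or reconsider the sample size.
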